## 8.0 GENERAL CONSIDERATIONS

In general, numerical variables in demographic and baseline characteristics will be summarized by displaying: n (non-missing sample size), mean, standard deviation, median, quartiles, maximum and minimum. The frequency and percentages (based on the non-missing sample size) of observed

levels will be reported for all categorical measures. Percentages will be calculated out of the total number of subjects per group.

Numerical effectiveness variables described above will be summarized displaying n, mean, median, standard deviation ([SD](#)), standard error (SE), quartiles, minimum, maximum.

All summary tables will be structured with a column for either treated or fellow eye.

No inferential statistics will be applied to baseline characteristics and safety variables unless specified otherwise.

In general, all data will be listed and sorted by treatment or fellow eye status, cohort number, site and subject, and when appropriate by visit number (or assessment date) as appropriate.

Most data manipulation, tables, figures, listings, and analysis will be documented in SAS programs and performed using SAS® Software version 9.4.

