7.3 STUDY ENDPOINTS

7.3.1 Safety and Tolerability Endpoints

Safety and tolerability of OpRegen treatment will be assessed by:

- Incidence and frequency of treatment emergent AEs
- Treatment emergent changes in the following variables:
 - Vital signs
 - Hematology/ Blood Chemistry/Urinalysis
 - Physical examination

- Ophthalmological evaluations including:
 - ✓ BCVA
 - ✓ Dilated Fundus Exam
 - ✓ IOP
 - ✓ SLE
 - ✓ SD-OCT
 - ✓ FA
 - ✓ Microperimetry
 - ✓ FAF
 - ✓ CFP

[REDACTED]

[REDACTED]

[REDACTED]

[REDACTED]

[REDACTED]

- [REDACTED]
- [REDACTED]
- [REDACTED]

[REDACTED]

- [REDACTED]

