8.2 ELIGIBILITY CRITERIA FOR COHORTS 1-3

8.2.1 Inclusion Criteria

1. Age 50 and older.
2. Diagnosis of dry (non-neovascular) age related macular degeneration in both eyes.
3. Funduscopy findings of dry AMD with progressive geographic atrophy in the macula,
[REDACTED]
4. Best corrected central visual acuity equal or less than 20/200 in the study eye by ETDRS vision testing.
5. Vision in the non-operated eye must be better than or equal to that in the operated eye.

6. Subjects with sufficiently good health to allow participation in all study-related procedures and complete the study follow-up period (based on medical records).
7. Ability to undergo a vitreoretinal surgical procedure under monitored anesthesia care.
8. Blood counts, blood chemistry, coagulation and urinalysis without abnormal significance.
9. Negative for HIV, HBC, and HCV. Negative for CMV IgM and EBV IgM.
10. Willing to defer donation of blood and tissues.
11. Able to understand study procedures and willing to sign informed consent

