21.2.1 Device Adverse Events of Special Interest

When present at the time of surgery the following AESI may be assessed for grading as follows:

- 21.2.1.1 MILD: Subject is aware of event or symptom but event/symptom is easily tolerated.
- 21.2.1.2 MODERATE: Subject experiences sufficient discomfort to interfere with or reduce his or her usual level of activity.
- 21.2.1.3 MODERATELY SEVERE: Subject experiences impairment (e.g. vision loss up to 3 lines) or a related event that may require an additional procedure
- 21.2.1.4 SEVERE: Significant impairment of functioning; subject is unable to carry out usual activities and/or the subject's life is at risk from the adverse event.

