**Table 1. Study Assessments**

Assessment	Time points	Primary Endpoints/ Safety	Efficacy Endpoints of Clinical Relevance
Best-Corrected Visual Acuity (BCVA)-ETDRS Retro illuminated 4-meter ETDRS Chart “R” for refraction followed by Chart “1” and “2” BCVA is reported in number of letters read correctly. First, the right eye is tested with Chart 1 and then the left eye is tested with Chart 2. Must be conducted by trained examiner (technician acceptable) and as per “BCVA Instructions Manual”.	[REDACTED]	√	√
Low Luminance Best Corrected Visual Acuity LL BCVA is measured by placing a 2.0-log-unit neutral density filter over the trial frame in front of the study eye and having the participant read the normally illuminated ETDRS chart using a different version of the chart. This test is optional as subjects with low vision will not be able to perform this test and is not applicable for Cohorts 1-3.	[REDACTED]		√
Spectral Domain Optical Coherence Tomography (SD-OCT) Images obtained by certified examiner (technician acceptable). Reading of images done by central reading center. Refer to Central Reading manual for instructions.	[REDACTED]	√	√
[REDACTED]	[REDACTED]	√	
Dilated Fundus Examination (peripheral retina, macula, choroid, optic nerve, retinal/detachment, retinal or vitreous hemorrhage, vitreous hemorrhage density, vitreous cells.)	[REDACTED]	√	

Assessment	Time points	Primary Endpoints/ Safety	Efficacy Endpoints of Clinical Relevance
Microperimetry Automated microperimetry to be performed in Cohort 3 (optional) and in Cohort 4. Must be conducted by certified examiner (technician is acceptable). Reading of images done by central reading center. Refer to Central Reading manual for instructions.		√	√
Fluorescein Angiography (FA) Standard procedure for detection of CNV . Must be conducted by certified examiner (technician is acceptable): at [REDACTED] to verify dry AMD and absence of neovascular (wet) AMD , and on final exam at end of study; optional FA during follow-up in cases of suspected conversion to wet AMD		√	
Intraocular Pressure (IOP) One IOP measurement per eye		√	
Slit Lamp Examination (Lids/Lashes, Conjunctiva, Cornea, Iris, Aqueous Cells, Aqueous Flare and Lens) Must be conducted by certified examiner (technician is acceptable)		√	

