### 7.1.10 Efficacy Analyses

All efficacy data will be listed for all subjects. Efficacy summaries will be presented for the Intent to Treat Population for all variables.

- Directional change in the geographic atrophy ([GA](#)) lesion area over time
- Overall change in the [GA](#) lesion area of the study eye over time using [FAF](#)
- Change from baseline over time in [BCVA](#) as measured by Early Treatment Diabetic Retinopathy Study ([ETDRS](#)) chart
- Change from baseline over time in Low Luminance [BCVA](#)
- Change from baseline over time in [IOP](#)

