## 11.0 SUMMARY TABLES, FIGURES AND DATA LISTINGS

### List of Tables

Table Number	Table Title
14.1.1	Subjects Disposition
14.1.2	Time in Study
14.1.3	Early Discontinuations
14.1.4.1	Demography screened subjects
14.1.4.2	Demography
14.1.6	Physical Examination
14.1.7	General Medical History
14.1.8	Concomitant Medications
14.1.9	Per Protocol Medications
14.1.10	AMD History
14.1.11	Ocular History
14.1.5	OpRegen Surgical Procedure
14.3.1.1.1	Frequency and Incidence of Treatment Emergent Adverse Events by MedDRA System Organ Class
14.3.1.1.2	Frequency and Incidence of Treatment Emergent Adverse Events by MedDRA System Organ Class and Preferred Term
14.3.1.2.2	Frequency and Incidence of Serious Treatment Emergent Adverse Events by MedDRA System Organ Class, Preferred Term
14.3.1.4.2	Frequency and Incidence of Treatment Emergent Adverse Events by Event Relationship to Per Protocol Treatment MedDRA System Organ Class, Preferred Term
14.3.1.8.2	Frequency and Incidence of Treatment Emergent Adverse Events by Ocular Toxicity MedDRA System Organ Class, Preferred Term
14.3.1.9.2	Frequency and Incidence of Treatment Emergent Adverse Events by Systemic Toxicity MedDRA System Organ Class, Preferred Term
14.3.3.2	Vital Signs
14.3.2	Laboratory results
14.2.1	Efficacy Geographic Atrophy
14.2.2	Efficacy Best Corrected Visual Acuity
14.2.3.1	Efficacy Intra-Ocular Pressure

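### BCVA is a protocol safety endpoint, but the SAP analyses it only as an efficacy change score, and no planned table counts the eyes with a large loss

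*SAP*

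**What the plan says.** **Protocol.** Safety and tolerability are the primary objective (7.2.1). Section 7.3.1 makes treatment-emergent change a safety endpoint for a list of variables. Under "Ophthalmological evaluations including" the first item is BCVA. Section 7.3.4 also lists BCVA for efficacy.

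**SAP, status of BCVA.** Table 1 ticks BCVA in both the safety and the efficacy columns and states that "BCVA is reported in number of letters read correctly". Section 3.2.1 names one ophthalmological safety variable, intraocular pressure (IOP); BCVA is not there. BCVA is analysed in 7.1.10 as change from baseline, and its table, figure and listing (14.2.2, 14.2.2 and 16.2.2) all carry an efficacy title.

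**SAP, statistics.** Section 8.0: "Numerical effectiveness variables described above will be summarized displaying n, mean, median, standard deviation", then "standard error (SE), quartiles, minimum, maximum". The same section gives treated and fellow eyes their own column. Section 7.1.10 adds "All efficacy data will be listed for all subjects".

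**Entry limits.** Cohorts 1 to 3 require "Best corrected central visual acuity equal or less than 20/200 in the study eye by ETDRS vision testing", with no lower limit in the visible criteria. Cohort 4 requires 29 to 64 letters (Protocol 8.3.1).

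**IOP.** It is a safety variable in SAP 3.2.1, but it appears in 7.1.10 among the efficacy analyses and in the list of tables as "Efficacy Intra-Ocular Pressure".

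**The concern.** Losing remaining sight in the operated eye is a harm that a safety reader will look for, most of all in Cohort 4, where the eyes still see usefully. The natural safety summary is a count: how many eyes lost a large amount, and how many were still down at the end. The planned statistics describe the centre, the spread and the single most extreme value. If most eyes gain a little and a few lose a lot, the mean and quartiles can look neutral or favourable, and the minimum is the same whether one eye or several reached it. With BCVA filed under efficacy, the safety tables for the primary objective would contain no measured acuity at all.

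**Working it through.** The documents give no calculated figure on this point, so there is none to reproduce. The cohort sizes add up: 3 + 3 + 6 + 12 = 24.

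**1. What the planned statistics show (letter changes assumed).** Quartiles use the SAS default definition.

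| Cohort 4, n = 12 | Mean | SD | Quartiles and median | Min | Max | Eyes losing 15 or more |
|---|---|---|---|---|---|---|
| 10 at +3, 2 at -15 | (30 - 30)/12 = 0.0 | sqrt(540/11) = 7.0 | +3, +3, +3 | -15 | +3 | 2 |
| 11 at +3, 1 at -15 | (33 - 15)/12 = 1.5 | sqrt(297/11) = 5.2 | +3, +3, +3 | -15 | +3 | 1 |

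Median, quartiles, minimum and maximum are identical in the two rows. The mean and SD differ, but with real scores that vary between eyes they do not convert back into a count.

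**2. How many losses leave the quartiles unmoved.** With n = 12 the lower quartile is the average of the 3rd and 4th ordered values, so up to two losing eyes do not touch it. With n = 24 it is the average of the 6th and 7th, so up to five do not. Example over all eyes: 3 lose 30 letters and 21 gain 5. The mean is (105 - 90)/24 = +0.6, the median and both quartiles are +5, and the minimum is -30.

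**3. Where nothing is hidden.** In a three-eye cohort with changes -30, +2 and +4, the minimum, median and maximum print every value.

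**4. What a count would add (Clopper-Pearson 95% CI).**

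- 0/12: 0% (0 to 26.5%)
- 1/12: 8.3% (0.2 to 38.5%)
- 2/12: 16.7% (2.1 to 48.4%)
- 3/24: 12.5% (2.7 to 32.4%)

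**5. Eyes that cannot register the loss.** The score counts letters read, so the largest recordable loss equals the baseline score. An eye starting at 0 to 14 letters can never show a 15-letter loss; one starting at 15 or more can. Every Cohort 4 eye (29 letters or more) can. For Cohorts 1 to 3 the baseline scores are not in the documents. If 3, 6 or 9 of those 12 eyes started below 15 letters, 9, 6 or 3 would be evaluable. The upper limit after zero observed losses would then be 33.6%, 45.9% or 70.8%, against 26.5% if all 12 were counted. A percentage over all eyes would therefore look more reassuring than the data allow.

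**6. The adverse event route.** Protocol 14.1 has observed changes reported as adverse events, but 21.1 makes an abnormal result an event only under conditions such as investigator-judged significance. The ocular toxicity scale (Protocol Table 6) has no row for acuity loss; vision enters only as blindness following keratitis or glaucoma. Line-loss wording such as "Subject experiences impairment (e.g. vision loss up to 3 lines) or a related event" belongs to the grading of device events, and the SAP lists no table of those events.

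**The case against.** The strongest reply is that nothing is lost. The minimum is tabulated, every eye is listed, and with 24 subjects a reader can count losses and follow them across visits in listing 16.2.2. The study is descriptive, with no formal testing. That much stands: the gap is in the summary tables, not in the data. It does not explain why a variable named as safety in the protocol and in SAP Table 1 is missing from SAP 3.2.1, or why the safety tables should leave the reader to count by hand.

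A reader might also infer more than the documents support:

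- *That only the mean is reported.* SAP 8.0 gives median, SD, SE, quartiles, minimum and maximum as well.
- *That fellow eyes are ignored.* SAP 8.0 gives them a column, and SAP 7.0 examines them in the same way as treated eyes.
- *That IOP has been dropped from safety.* SAP 3.2.1 keeps it, its maximum is a planned statistic, and adverse events by ocular toxicity have their own table (14.3.1.8.2). Only the efficacy label is inconsistent.
- *That percent change in BCVA breaks down at zero letters.* SAP 4.1.2 is a general formula; 7.1.10 plans only change from baseline for BCVA.
- *That a floor distorts half the sample.* It affects only eyes that start very low. The Cohort 4 criterion pairs 29 letters with 20/250, so an eye near 20/200 has room to lose 15 letters. Scoring of off-chart vision may also be covered in the BCVA manual that Table 1 cites, which is not available here.
- *That the protocol sets a three-line threshold for BCVA.* Its line boundaries grade device events at surgery, with up to 3 lines in grade 3 and more than 3 in grade 4.

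**Conclusion.** The point holds in two parts. First, the SAP departs from the protocol and from its own Table 1 by omitting BCVA from the safety variables and analysing it only under efficacy. Secondly, no visible table states the number of eyes with a large loss. Up to two such eyes in Cohort 4, or five among all 24, can leave both quartiles unchanged. In the worked example a mean change of 0.0 coexists with 2/12 eyes losing 15 letters (16.7%, CI 2.1% to 48.4%).

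The letter changes and the 15-letter threshold are assumptions; reading 15 letters as three lines further assumes five letters per line. How many Cohort 1 to 3 eyes start below 15 letters is unknown, and redacted text may hold more. The consequence is an incomplete summary for the primary objective, recoverable from the listings. It should be corrected before database lock but does not threaten the study.

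**What to change.** 1. Restore BCVA to SAP 3.2.1 as a safety variable, keeping its efficacy analysis.
2. Add one safety table, by cohort and overall, for study and fellow eyes. Give the number and percent of eyes with a loss of at least a pre-specified number of letters (15 proposed) at any post-implantation visit and at the last visit, with exact 95% CIs. Both time points are needed: the any-visit count also picks up short-lived drops and test variability, for which the fellow eye gives a reference. SAP 8.0 excludes inferential statistics for safety variables unless specified, so the text should state that these intervals are intended.
3. In the same table show the number of eyes whose baseline is below the threshold, leave them out of the denominator, and report them separately. Use off-chart acuity only where source records already hold it. SAP 4.0 describes all 24 eyes as treated, so a new data field could not recover past values.
4. Relabel the IOP table, figure and listing as safety, to agree with SAP 3.2.1.

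SAP 2.0 allows revisions before database lock. As the study is open-label, record when the threshold was fixed. The cost is one SAP paragraph and one table from letter scores already collected. The downside is one more descriptive table with wide intervals.

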### 3.3 Study Hypothesis

As this is an open label, phase I/IIa dose escalation, safety, tolerability, and preliminary efficacy study, neither power assessment, nor formal hypotheses testing were planned for study outcome measures. However, for purposes of data analyses and this SAP, the Sponsor hypothesizes that implantation of OpRegen to subjects with advanced dry-form AMD with GA is safe, well-tolerated and provides evidence of preliminary efficacy based on pre-specified functional and structural assessments.

The primary hypothesis is that there will be no dose-limiting toxicity (DLT) and that implantation of OpRegen to subjects with progressive dry-form AMD with GA will be safe and well-tolerated. For this study DLT is defined as an SAE determined to be product related.

A secondary null hypothesis is that there will be no difference in disease progression, as measured by retinal function and structure, between the treated and untreated regions in the treated eye and between the treated and untreated eye of a subject.

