#### 4.1.2 Baseline and Change from Baseline

Unless indicated otherwise, change from baseline (CFB) will be calculated as follows, where the baseline assessment is the last assessment before OpRegen injection:

$$\text{CFB} = \text{Value at Visit} - \text{Baseline}$$

Percent change from baseline (PCFB) will be calculated as follow:

$$\text{PCFB (\%)} = 100 * (\text{Value at Visit} - \text{Baseline}) / \text{Baseline}$$

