## 6.4 Descriptive Statistics

All measured variables and derived parameters will be listed individually and if appropriate, presented in summary tables by dose regimen group and overall, providing sample size, absolute and relative frequency for categorical variables, or sample size, arithmetic mean, standard deviation, median, minimum, and maximum for continuous variables. [Confidence intervals](#) will be presented for the efficacy endpoints for exploratory purposes only.

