Measurements of retinal structure and function made on the non-treated eye of each subject will also be examined in the same way as for the treated eye to evaluate the extent to which placebo effects or unexpected temporal trends may be contributing to observed changes in retinal function.

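### The SAP states a between-eye null but summarises each eye separately, so its tables cannot show the precision of the treated-minus-fellow difference

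*SAP*

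**What the plan says.** **The comparison.** SAP 3.3 states a secondary null of no difference in disease progression "between the treated and untreated regions in the treated eye and between the treated and untreated eye of a subject". Protocol 22.14 adds that the untreated eyes are a good comparator for how fast GA enlarges.

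**The reporting.** SAP 4.1.2 defines change and percent change from baseline, "where the baseline assessment is the last assessment before OpRegen injection". SAP 7.0 says that measurements on the "non-treated eye of each subject will also be examined in the same way as for the treated eye". SAP 8.0 says "All summary tables will be structured with a column for either treated or fellow eye", and lists n, mean, median, SD, SE, quartiles and range for the numerical effectiveness variables. It also says that "all data will be listed and sorted by treatment or fellow eye status, cohort number, site and subject". SAP 6.4 promises exploratory confidence intervals for the efficacy endpoints.

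**The endpoint lists.** SAP 3.2.4 names ten efficacy endpoints. SAP 7.1.10 opens with "All efficacy data will be listed for all subjects. Efficacy summaries will be presented for the Intent to Treat Population for all variables" and then gives five bullets: directional GA change, overall change in GA "lesion area of the study eye over time using" FAF, BCVA, low-luminance BCVA, and IOP. SAP 6.4 says "All measured variables and derived parameters will be listed individually and if appropriate, presented in summary tables by dose regimen group and overall". SAP 7.0 ties the tables, listings and figures to Section 11. It also promises table shells, which are not in the documents supplied.

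**The concern.** A null about two eyes of one subject concerns a within-subject difference. The visible SAP turns it into two separate descriptions, one per eye. The trial has no control arm, and the fellow eye is its only concurrent between-eye comparator. The quantity that speaks most directly to the stated null would therefore appear in the summary tables without an interval.

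The second issue is completeness. Endpoints that the SAP still lists should have a stated summary and an output to appear in. Six of the ten have neither by name, so a programmer could follow the general promise of full coverage or follow Section 11, and the two lead to different reports.

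**Working it through.** **1. Sample size.** SAP 6.0 plans 24 treated eyes. The cohort sizes in SAP 4.0 give 3 + 3 + 6 + 12 = 24, which agrees. No power, SD or between-eye correlation is stated, so results are in units of the SD of change, with the correlation ρ varied as an assumption.

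**2. What two columns can give.** Let each eye's change have SD σ (assumed equal in both eyes).

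- Mean difference = mean(treated) − mean(fellow). This can be read from the columns if every subject has both eyes measured.
- Its variance = 2σ²(1 − ρ)/n. The columns give σ and n but not ρ.
- 95% half-width for one eye = t(0.975, n−1) × √(1/n) × σ.
- 95% half-width for the paired difference = t(0.975, n−1) × √(2(1 − ρ)/n) × σ.

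**3. Cohort 4, n = 12, t(0.975, 11) = 2.201.** One eye alone: 2.201 × √(1/12) = 0.635σ. Treated minus fellow:

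| ρ (assumed) | √(2(1 − ρ)/12) | Half-width (σ) |
|---|---|---|
| 0 | 0.408 | 0.899 |
| 0.3 | 0.342 | 0.752 |
| 0.5 | 0.289 | 0.635 |
| 0.7 | 0.224 | 0.492 |
| 0.8 | 0.183 | 0.402 |

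The same pair of columns fits intervals that differ by a factor of 0.899/0.402 = 2.24 over this range.

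**4. Cohorts 1 and 2, n = 3, t(0.975, 2) = 4.303.** At ρ = 0.5 the half-width is 4.303 × √(1/3) = 2.484σ, too wide to be useful.

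**5. Endpoint tally.** SAP 3.2.4 set against 7.1.10 and the Section 11 titles:

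| Endpoint in 3.2.4 | Item in 7.1.10 | Own title in Section 11 |
|---|---|---|
| Directional GA change | yes | yes (GA) |
| Overall GA area, SD-OCT and FAF | FAF only | yes (GA) |
| BCVA | yes | yes |
| Low-luminance BCVA | yes | no; could sit in BCVA outputs |
| Microperimetry | no | no |
| Reading speed | no | no |
| Correlation of imaging metrics | no | no |
| Function–structure correlation | no | no |
| NEI VFQ-25 | no | no |
| FRI Index | no | no |

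Four are itemised, and six have neither an item nor a title. Section 11 titles 11 efficacy outputs (3 tables, 4 figures, 4 listings): 5 for GA, 3 for BCVA and 3 for IOP, which SAP 3.2.1 classes as safety. None of the 20 listing titles names any of the six.

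**The case against.** **The plan is descriptive by choice.** SAP 7.0 says the numbers rule out definitive assessment by formal testing. It names other methods instead: comparison with between-visit variation within a subject and with previously studied populations, applied to both eyes. This stands. The absence of a test is no fault, and it would be wrong to infer that the fellow eye is ignored. But a mean difference with an exploratory interval is also descriptive, and the plan already promises exploratory intervals.

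**The intervals do have an object.** A reader might infer that the confidence intervals in SAP 6.4 attach to nothing. They attach to the efficacy endpoints, most of which are worded as changes over time, and 4.1.2 defines change from baseline. What is missing is narrower: an interval for the between-eye contrast.

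**The listings contain the pairs.** This also stands. Subject-level listings sorted by eye would let a reader compute the differences for GA and BCVA. The spread in step 3 therefore describes the summary tables, not what can be recovered from the whole report.

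**Nothing has been dropped.** SAP 7.1.10 promises, without qualification, that all efficacy data will be listed and all variables summarised. All ten endpoints remain in 3.2.4, and the unseen table shells may hold more detail. Limited collection may also explain some omissions: Table 1 makes microperimetry optional in Cohort 3, makes reading speed mandatory only for subjects proficient in English, and excludes Cohorts 1–3 from FRI. So the six cannot be called withdrawn. The inconsistency remains, because the promise is followed by a five-item list and 7.0 points to Section 11. For the two correlation endpoints a listing is not enough: no coefficient, pair of variables or visit is named in the visible text.

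**Selective reporting.** A reader might infer it, because the trial is open-label and the SAP, dated 12 October 2022, describes dosing in the past tense. The documents do not support that inference. Nothing in them links the choice of outputs to results.

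**Conclusion.** The main point holds for the between-eye half of the secondary null. The visible SAP defines no treated-minus-fellow difference, and its summary tables would show the point estimate (given complete pairs) without its precision. In Cohort 4 the unreported half-width could lie anywhere from 0.90σ at ρ = 0, through 0.64σ at ρ = 0.5, to 0.40σ at ρ = 0.8. This rests on equal SDs in the two eyes and on assumed correlations; the documents supply neither. No planned decision depends on the interval, so the loss is in interpretability of the main concurrent comparison.

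The six endpoints are a secondary point about internal consistency: SAP 3.2.4, 7.1.10 and Section 11 do not match. The conclusion is limited to visible text, and the shells could resolve part of it. The SAP is labelled an initial draft and allows revision before database lock, so its own rules permit the repair.

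**What to change.** **Between-eye contrast, in SAP 7.1.10 and Section 11:**

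- For Cohort 4, add the subject-level treated-minus-fellow difference in annual GA enlargement rate. Section 11 already titles a rate figure and listing; state how the rate is derived.
- Add the same difference in GA-area change at the main short-term visit. Give each difference its mean and an exploratory paired-t 95% interval, labelled descriptive.
- Note beside it that Cohort 4 mixes two formulations and two delivery systems.
- For Cohorts 1 and 2 show individual differences only. Label any all-cohort pooled estimate as mixing doses and BCVA strata.
- BCVA may be shown as supportive, beside both eyes' baselines, because the study eye is the worse eye by design.

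**Endpoint lists.** Reconcile 3.2.4, 7.1.10 and Section 11. Either add the six endpoints and SD-OCT GA area, each limited to the subjects in whom it is collected, or document their removal with the reason. Protocol 22.1 requires a protocol amendment if the removal is judged a major modification.

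**Population label.** Section 7.1.10 uses an Intent to Treat Population that SAP 6.1 does not define. Replace it with the All Treated Population of 6.1.

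**Cost.** SAP wording and a few added tables and listings from data already planned for collection, with no added subjects or procedures. The downside is that the exploratory intervals will be wide and should be read as such.
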